2.4 Safety Statistical Analysis

2.4.1 Onset Status of Adverse Drug Reactions or Infections (Exhibit 2)

Statistical Analysis Set	Safety-evaluable patients in clinical studies before approval (total of patients in clinical studies in Japan used for safety evaluation stated in the Adverse Drug Reactions section of the package insert) and this special drug use surveillance														
Details of Statistical Analysis	
Compile the following items for the prior-approval status and per survey unit period of the special drug use surveillance.
 
Statistical analysis of ‘number of study sites,’ ‘number of surveyed patients,’ ‘number of patients with ADRs,’ and ‘number of ADRs’ should cover safety-evaluable patients locked during each survey unit period.
 
  
 Item Name	Details of Statistical Analysis	
   
 Number of study sites	Number of medical institutions that have collected eCRFs	
 
 Number of surveyed patients	Number of safety-evaluable patients.	
 
 Number of patients with ADRs	Number of patients in which ADRs occurred.	
 
 Number of ADRs	Number of ADRs that occurred. Every PT occurring should be counted as one event.	
 
 Rate of patients with ADRs	Calculated by the following equation: $[\text{Number of Patients with ADRs}] / [\text{Number of Safety-Evaluable Patients}] \times 100$	
 
 ADR type	 
The calculation method in performing each analysis should be as follows:
 
[Number of patients with ADRs]
 
 Number of patients in which ADRs occurred. 
[Number of ADRs]
 
 Number of ADRs that occurred. If the same ADR occurs more than once in the same patient, a total of frequencies of the ADR should be counted. 
[Rate of patients with ADRs]
 
 Calculated by the following equation: $[\text{Number of Patients with ADRs}] / [\text{Number of Safety-Evaluable Patients}] \times 100$. 
[ADR type]
 
 ADRs should be replaced by MedDRA terms. Categorize by SOC and compile ADRs by PT in each category. If SOC is ‘Investigations,’ classify by HLG (sort by HLG code in ascending order but without outputting) and compile ADRs by PT. 
 At SOC level, the numbers and rates of patients with ADRs should be presented by SOC internationally agreed order. If the same SOC occurs more than once in the same patient, ADRs should be counted as one patient in the SOC. At PT level, the numbers and rates of patients with ADRs should be presented by PT code in 	
  
	Item Name	Details of Statistical Analysis	Number of study sites	Number of medical institutions that have collected eCRFs	Number of surveyed patients	Number of safety-evaluable patients.	Number of patients with ADRs	Number of patients in which ADRs occurred.	Number of ADRs	Number of ADRs that occurred. Every PT occurring should be counted as one event.	Rate of patients with ADRs	Calculated by the following equation: $[\text{Number of Patients with ADRs}] / [\text{Number of Safety-Evaluable Patients}] \times 100$	ADR type	
The calculation method in performing each analysis should be as follows:
 
[Number of patients with ADRs]
 
 Number of patients in which ADRs occurred. 
[Number of ADRs]
 
 Number of ADRs that occurred. If the same ADR occurs more than once in the same patient, a total of frequencies of the ADR should be counted. 
[Rate of patients with ADRs]
 
 Calculated by the following equation: $[\text{Number of Patients with ADRs}] / [\text{Number of Safety-Evaluable Patients}] \times 100$. 
[ADR type]
 
 ADRs should be replaced by MedDRA terms. Categorize by SOC and compile ADRs by PT in each category. If SOC is ‘Investigations,’ classify by HLG (sort by HLG code in ascending order but without outputting) and compile ADRs by PT. 
 At SOC level, the numbers and rates of patients with ADRs should be presented by SOC internationally agreed order. If the same SOC occurs more than once in the same patient, ADRs should be counted as one patient in the SOC. At PT level, the numbers and rates of patients with ADRs should be presented by PT code in
Item Name	Details of Statistical Analysis														
Number of study sites	Number of medical institutions that have collected eCRFs														
Number of surveyed patients	Number of safety-evaluable patients.														
Number of patients with ADRs	Number of patients in which ADRs occurred.														
Number of ADRs	Number of ADRs that occurred. Every PT occurring should be counted as one event.														
Rate of patients with ADRs	Calculated by the following equation: $[\text{Number of Patients with ADRs}] / [\text{Number of Safety-Evaluable Patients}] \times 100$														
ADR type	
The calculation method in performing each analysis should be as follows:
 
[Number of patients with ADRs]
 
 Number of patients in which ADRs occurred. 
[Number of ADRs]
 
 Number of ADRs that occurred. If the same ADR occurs more than once in the same patient, a total of frequencies of the ADR should be counted. 
[Rate of patients with ADRs]
 
 Calculated by the following equation: $[\text{Number of Patients with ADRs}] / [\text{Number of Safety-Evaluable Patients}] \times 100$. 
[ADR type]
 
 ADRs should be replaced by MedDRA terms. Categorize by SOC and compile ADRs by PT in each category. If SOC is ‘Investigations,’ classify by HLG (sort by HLG code in ascending order but without outputting) and compile ADRs by PT. 
 At SOC level, the numbers and rates of patients with ADRs should be presented by SOC internationally agreed order. If the same SOC occurs more than once in the same patient, ADRs should be counted as one patient in the SOC. At PT level, the numbers and rates of patients with ADRs should be presented by PT code in 														

		ascending order. If the same PT occurs more than once in the same patient, ADRs should be counted as one patient in the PT.
	Cumulative total for special drug use surveillance	A respective total of the numbers of study sites and patients per survey unit period. Do not double-count the same medical institution when counting the number of study sites.
Figure/Table No.	Table 2.4.1	

2.4.2 Onset Status of Adverse Drug Reactions/Infections in Safety-Unevaluable Patients

Statistical Analysis Set	Safety-unevaluable patients in this specified drug use surveillance	
Details of Statistical Analysis	Compile the following items.	
	Item Name	Details of Statistical Analysis
	Number of study sites	Number of medical institutions that have collected eCRFs
	Number of surveyed patients	Number of safety-unevaluable patients.
	Number of patients with ADRs	Number of patients in which ADRs occurred.
	Number of ADRs	Number of ADRs that have occurred. Every PT occurring should be counted as one event.
	ADR type	
The calculation method in performing each analysis should be as follows:
 
[Number of patients with ADRs]
 
 Number of patients in which ADRs occurred. 
[Number of ADRs]
 
 Number of ADRs that occurred. If the same ADR occurs more than once in the same patient, a total of frequencies of the ADR should be counted. 
[ADR type]
 
 ADRs should be replaced by MedDRA terms. Categorize by SOC and compile ADRs by PT in each category. If SOC is 'Investigations,' classify by HLG (sort by HLG code in ascending order but without outputting) and compile ADRs by PT. 
 At SOC level, the numbers of patients with ADRs should be presented by SOC internationally agreed order. If the same SOC occurs more than once in the same patient, ADRs should be counted as one patient in the SOC. 
At PT level, the numbers of patients with ADRs should be presented by PT code in ascending order. If the same PT occurs more than once in the same patient, ADRs should be counted as one patient in the PT.

Figure/Table No.	Table 2.4.2	

2.4.3 Onset Status of AE

Statistical Analysis Set	Safety-evaluable patients in this special drug use surveillance	
Details of Statistical Analysis	The compilation method is the same as described in section 2.4.1. However, adverse drug reactions should be replaced by adverse events.	
Figure/Table No.	Table 2.4.3	

2.4.4 Onset Status of Adverse Events in Safety-Unevaluable Patients

Statistical Analysis Set	Safety-unevaluable patients in this specified drug use surveillance
Details of Statistical Analysis	Compilation method is the same as described in section 2.4.2. However, adverse drug reactions should be replaced by adverse events.
Figure/Table No.	Table 2.4.4

2.4.5 Onset Status of Adverse Drug Reactions or Infections by Seriousness, Onset Time, and Outcome

Statistical Analysis Set	Safety-evaluable patients in this special drug use surveillance														
Details of Statistical Analysis	
Categorize ADRs by the following categories for each item and compile ADR types.
 
  
 Item Name	Details of Statistical Analysis	
   
 Number of patients	Compile the number of patients with ADRs.	
 
 Number of ADRs	At SOC, the number of ADRs should be compiled by totaling associated PTs that occurred. At PT level, every PT occurring should be counted as one event.	
  
 
  
 Item Name	Category	
   
 Seriousness	Serious, Not serious	
 
 Onset time	1 to 15 days, 16 to 30 days, 31 to 90 days, 91 to 180 days, 181 to 360 days, 361 days or over, Unknown	
 
 Outcome	Resolved, Resolving, Not resolved, Resolved with sequelae, Death, Unknown	
  
	Item Name	Details of Statistical Analysis	Number of patients	Compile the number of patients with ADRs.	Number of ADRs	At SOC, the number of ADRs should be compiled by totaling associated PTs that occurred. At PT level, every PT occurring should be counted as one event.	Item Name	Category	Seriousness	Serious, Not serious	Onset time	1 to 15 days, 16 to 30 days, 31 to 90 days, 91 to 180 days, 181 to 360 days, 361 days or over, Unknown	Outcome	Resolved, Resolving, Not resolved, Resolved with sequelae, Death, Unknown
Item Name	Details of Statistical Analysis														
Number of patients	Compile the number of patients with ADRs.														
Number of ADRs	At SOC, the number of ADRs should be compiled by totaling associated PTs that occurred. At PT level, every PT occurring should be counted as one event.														
Item Name	Category														
Seriousness	Serious, Not serious														
Onset time	1 to 15 days, 16 to 30 days, 31 to 90 days, 91 to 180 days, 181 to 360 days, 361 days or over, Unknown														
Outcome	Resolved, Resolving, Not resolved, Resolved with sequelae, Death, Unknown														
Figure/Table No.	Table 2.4.5														

2.4.6 Onset Status of Adverse Events by Seriousness, Onset Time, and Outcome

Statistical Analysis Set	Safety-evaluable patients in this special drug use surveillance										
Details of Statistical Analysis	
Categorize AEs by the following categories for each item and compile AE types. The compilation method of AE types is the same as described in section 2.4.5. However, adverse drug reactions should be replaced by adverse events.
 
  
 Item Name	Category	
   
 Seriousness	Serious, Not serious	
 
 Onset time	1 to 15 days, 16 to 30 days, 31 to 90 days, 91 to 180 days, 181 to 360 days, 361 days or over, Unknown	
 
 Outcome	Resolved, Resolving, Not resolved, Resolved with sequelae, Death, Unknown	
 
 Causal relationship with the Drug	 Related, Not related, Unevaluable If AEs (LLTs) occur more than once in the same patient, they should be counted as one event in the following order of priority: (1) Related, (2) Unevaluable, (3) Not related 	
  
	Item Name	Category	Seriousness	Serious, Not serious	Onset time	1 to 15 days, 16 to 30 days, 31 to 90 days, 91 to 180 days, 181 to 360 days, 361 days or over, Unknown	Outcome	Resolved, Resolving, Not resolved, Resolved with sequelae, Death, Unknown	Causal relationship with the Drug	Related, Not related, Unevaluable If AEs (LLTs) occur more than once in the same patient, they should be counted as one event in the following order of priority: (1) Related, (2) Unevaluable, (3) Not related
Item Name	Category										
Seriousness	Serious, Not serious										
Onset time	1 to 15 days, 16 to 30 days, 31 to 90 days, 91 to 180 days, 181 to 360 days, 361 days or over, Unknown										
Outcome	Resolved, Resolving, Not resolved, Resolved with sequelae, Death, Unknown										
Causal relationship with the Drug	Related, Not related, Unevaluable If AEs (LLTs) occur more than once in the same patient, they should be counted as one event in the following order of priority: (1) Related, (2) Unevaluable, (3) Not related										
Figure/Table No.	Table 2.4.6										

2.4.7 Onset Status of Adverse Drug Reactions (Bleeding-Related Events) by Seriousness, Onset Time, and Outcome

Statistical Analysis Set	Safety-evaluable patients in this special drug use surveillance
Details of Statistical Analysis	
Categorize adverse drug reactions (bleeding-related events) by the following categories for each item, and count the types of adverse drug reactions (bleeding-related events). The categories and the compilation method of adverse drug reactions are the same as described in section 2.4.5.

Figure/Table No.	Table 2.4.7

2.4.8 Rate of Patients of Adverse Drug Reactions or Infections by Patient Demographics and Treatment

Details

Statistical Analysis Set	Safety-evaluable patients in this special drug use surveillance	
Details of Statistical Analysis	Categorize ADRs by the following categories for each item and compile the rate of patients with ADRs.	
	Item Name	Category
	Sex	Male, Female
	Age	Minimum age to 64 years, 65 to 74 years, 75 years to maximum age, Unknown
	BMI	Less than 18.5 kg/m ² , 18.5 to less than 25 kg/m ² , 25 to less than 30 kg/m ² , 30 kg/m ² or over, unknown
	Complications	No, Yes
	Complication breakdown	Hypertension, Diabetic, Liver disorder, Kidney disorder, Cardiac disorders Cerebrovascular diseases, Bleeding-related event, Others
	Fasting triglyceride at baseline (mg/dL)	Less than 150 mg/dL, 150 to less than 400 mg/dL, 400 to less than 500 mg/dL, 500mg/dL or over, Not measured
		Less than 150 mg/dL, 150 to less than 400mg/dL, 400 to less than 500 mg/dL, 500 to less than 750 mg/dL, 750 mg/dL or over, Not measured
	Random triglyceride at baseline (mg/dL)	Less than 150 mg/dL, 150 to less than 400 mg/dL, 400 to less than 500 mg/dL, 500mg/dL or over, Not measured
		Less than 150 mg/dL, 150 to less than 400mg/dL, 400 to less than 500 mg/dL, 500 to less than 750 mg/dL, 750 mg/dL or over, Not measured
	Initial dose	2 g, 4 g, other
	Breakdown of presence of change in daily dose	2 g → 4 g, 4 g → 2 g, Other
	Presence or absence of concomitant antihyperlipidemic drug use (during observation period)	No, Yes

	Breakdown of concomitant antihyperlipidemic drugs (during observation period)	statins drugs, fibrate drugs, intestinal transporter inhibitors, anion-exchange resin, nicotinic acid derivatives, probucol, ethyl icosapentate (EPA), others
	Presence or absence of concomitant anticoagulant/antiplatelet drug use (during observation period)	No, Yes
	Breakdown of concomitant anticoagulant/antiplatelet drugs (during observation period)	Anticoagulant drugs, antiplatelet drugs
Figure/Table No.	Table 2.4.8	

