9.6 Adverse Events (AEs)

1) Survey items

Presence or absence of AE (see Table 1), AE name, date of onset, seriousness and reason for seriousness (see Table 2), action taken to the Drug, date of determination of outcome, outcome, and causal relationship to the Drug* (see Table 3)

If the outcome is not resolved or unknown and the causal relationship is determined as unevaluable, follow-up survey should be conducted to some extent possible.

*If causal relationship to the Drug is determined as not related, reasons that may constitute the rationale for determination should be collected if it is unevaluable.

2) Survey timing

Period from baseline to Month 12 (or discontinuation of treatment)

3) Priority survey item

Bleeding-related events occurring after baseline are set as a priority survey item. If any bleeding-related event is reported as an AE, laboratory test values related to bleeding should be separately collected.

Table 1 Definition of Adverse Event

An adverse event (AE) is any untoward medical occurrence in a patient administered a medicinal product and which does not necessarily have to have a causal relationship with this treatment.
 
An AE can therefore be any unfavorable and unintended sign (including an abnormal laboratory finding, for example), symptom, or disease temporally associated with the use of a medicinal product, whether or not considered related to the medicinal product.
 
The following should be also handled as an AE:
 
• A symptom or other problem occurring in an infant breastfed from a mother taking the medicinal product• A symptom or other problem occurring in a child administered the medicinal product• A symptom or other problem occurring in a patient administered or taking more than the approved dose of the medicinal product
--

Table 2 Seriousness Criteria

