10.4.1 Onset Status of Adverse Events

Compile the incidence of AEs occurring during the observation period, in terms of, e.g., causal relationship with the Drug, type, seriousness. Note that bleeding-related events should be separately compiled because such events are set as a priority survey item.

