10.4.2 Factors Likely to Affect Safety

Compile the incidence of ADRs occurring during the observation period, by stratification variables: patient baseline characteristics (sex, age, presence or absence of renal

dysfunction, presence or absence of hepatic dysfunction, etc.) and treatment regimen (administration of the Drug, administration of concomitant medications such as anticoagulant drugs, antiplatelet drugs).

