1.0 Definitions of Terms

1.1 Definitions

Item	Definition
Survey unit period (periodic safety report)	Periodic Safety Report 1: July 22, 2012 to January 21, 2013 Periodic Safety Report 2: January 22, 2013 to July 21, 2013 Periodic Safety Report 3: July 22, 2013 to January 21, 2014 Periodic Safety Report 4: January 22, 2014 to July 21, 2014 Periodic Safety Report 5: July 22, 2014 to July 21, 2015 Periodic Safety Report 6: July 22, 2015 to July 21, 2016 Periodic Safety Report 7: July 22, 2016 to July 21, 2017 Periodic Safety Report 8: July 22, 2017 to July 21, 2018
Drug	Lotriga Granular Capsules
SOC	System organ class of MedDRA.
HLGT	High level group term of MedDRA.
PT	Preferred term of MedDRA.
LLT	Lowest level term of MedDRA.
Enrolled patient	A patient approved for enrollment in the Study.
Patient with eCRF collected	An enrolled patient whose eCRF was submitted via CCI .
Patient with eCRF uncollected	An enrolled patient other than a patient with eCRF collected.
Locked patient	A patient who has completed the approval process in the PMS system.
Unlocked patient	A patient with eCRF collected other than a locked patient.
Safety-evaluable patient	A locked patient included in safety evaluation.
Safety-unevaluable patient	A locked patient excluded from safety evaluation.
Efficacy-evaluable patient	A safety-evaluable patient included in efficacy evaluation.
Efficacy-unevaluable patient	A safety-evaluable patient excluded from efficacy evaluation.
ADR	An abbreviated form of the term ‘adverse drug reaction or infection.’ Refers to an adverse event other than those judged by the investigator as ‘not related’ in causality to the Drug. In this plan, ‘adverse drug reactions or infections’ is used in headings, and ‘ADRs’ is used in the text and tables.
Serious adverse event (SAE)	[Prior-approval data] An adverse event (AE) judged as ‘serious’ by the trial investigator. [Surveillance data] An adverse event (AE) judged as ‘serious’ by the investigator. Note that events listed in the separate MedDRA code list of the Takeda Medically Significant AE List should be treated as serious even if judged as

Item	Definition
	'not serious' by the investigator.
Bleeding-related event	An event falling under Standardized MedDRA Query (SMQ) code 20000038 (hemorrhagic SMQ [narrow scope]).

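### Bleeding is the priority safety item, but the SAP groups it as an outcome only among adverse drug reactions, so no table counts each patient with any bleeding-related adverse event once

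*SAP*

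**What the plan says.** **Protocol.** Section 9.6 states: "Bleeding-related events occurring after baseline are set as a priority survey item". It adds a collection rule: "If any bleeding-related event is reported as an AE, laboratory test values related to bleeding should be separately collected". Section 10.4.1, headed as the onset status of AEs, asks for AE incidence and names causal relationship, type and seriousness as examples of how to break it down. It then says: "Note that bleeding-related events should be separately compiled because such events are set as a priority survey item". ADRs come in the next section, 10.4.2: "Compile the incidence of ADRs occurring during the observation period, by stratification variables". The stratification variables there include anticoagulant and antiplatelet use.

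**SAP definitions (1.1).** A bleeding-related event is "An event falling under Standardized MedDRA Query (SMQ) code 20000038", narrow scope, with no condition on causality. An ADR is defined by exclusion: "Refers to an adverse event other than those judged by the investigator as" not related to the Drug. Related and unevaluable events are therefore both ADRs.

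**SAP tables.** Section 2.4.7 reads: "Categorize adverse drug reactions (bleeding-related events) by the following categories for each item, and count the types of adverse drug reactions (bleeding-related events". Section 2.4.21 tabulates bleeding-related ADRs by anticoagulant and antiplatelet group. Sections 2.4.3 and 2.4.6 tabulate all AEs, the latter also by causality, and 2.4.37 tabulates serious AEs with causally denied ones in brackets. None of these three groups the bleeding terms. Section numbers are those of the current SAP, the one with eight periodic safety report periods. The older versions in the same file also have bleeding tables for ADRs only (2.4.7 and 2.4.13).

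**The concern.** The protocol places the bleeding instruction in its AE section, where causality is one way to break events down. The SAP turns causality into an entry condition for both bleeding tables. Followed exactly, it reports how many patients had a bleeding ADR but not how many patients bled.

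This matters because the survey has no control arm, and the grouped count of its priority item would rest entirely on the investigator's causality call. Protocol Table 3 allows a judgement of not related when other factors, concomitant medications among them, adequately explain the event. Bleeding in a patient on an anticoagulant or antiplatelet drug could be classed that way, and Protocol 3.2 expects about 10% of patients to use such drugs. A total that does not depend on the causality call would be a useful companion to the ADR count.

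**Working it through.** **1. Where the bleeding query is used (SAP 2.1 to 2.5.6).**

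| SAP section | Role of bleeding | Causality scope | One patient total for bleeding? |
|---|---|---|---|
| 2.4.7 | Outcome | ADRs only | Yes, for ADRs (method of 2.4.5) |
| 2.4.21 | Outcome, by co-medication group | ADRs only | For ADRs, within group |
| 2.4.3 | None; single preferred terms (PTs) visible | All AEs | No |
| 2.4.6 | None; single PTs visible by causality | All AEs | No |
| 2.4.37 | None; single PTs visible if serious | All serious AEs | No |
| 2.2, 2.4.8, 2.4.19 | Baseline complication | Not an outcome | No |

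**2. Why the PT rows do not give the total.** The counting rule in 2.4.1, carried into 2.4.3, is: "If the same PT occurs more than once in the same patient, ADRs should be counted as one patient in the PT". Patients are counted once within a PT and once within a system organ class (SOC). Neither is a bleeding grouping: the hemorrhage examples in Protocol 4.0 include gastrointestinal, urinary, respiratory and ocular sites. A patient with two bleeding PTs appears in two rows.

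**3. What a reader could still bound.** Let A be the bleeding-ADR patients (2.4.7), r the bleeding-PT rows of 2.4.3, and U the sum of the bleeding-PT counts judged not related (2.4.6).

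- Lower bound: the larger of A and max(r), because every bleeding-ADR patient is also a bleeding-AE patient.
- Upper bound: the smaller of sum(r) and A + U.

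Invented rows for illustration: r = 6, 5, 4, 2 and A = 12.

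- Lower bound: max(12, 6) = 12, and 12/3,000 = 0.40%.
- Upper bound: sum(r) = 17. Twelve ADR patients fill at least 12 of the 17 row entries, so U is at most 5 and A + U at most 17. The bound is 17 at most, and 17/3,000 = 0.57%.

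**4. Scale.** Inputs from Protocol 3.1 and 3.2: target 3,000 patients; 0.4% bleeding-related ADRs, reported from surveillance of EPA products and taken here as a share of patients. Expected bleeding-ADR patients: 3,000 × 0.004 = 12.

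Let g be the share of patients who bled whose bleeding events were all judged not related. The documents do not give g, so it is assumed. Then total = 12/(1 − g) and missing = 12/(1 − g) − 12.

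| g (assumed) | Total who bled | Missing from 2.4.7 | Rate, rounded count/3,000 (exact 95% CI) |
|---|---|---|---|
| 0% | 12 | 0 | 0.40% (0.21 to 0.70) |
| 10% | 13.3 | 1.3 | 0.43% (0.23 to 0.74) |
| 30% | 17.1 | 5.1 | 0.57% (0.33 to 0.91) |
| 50% | 24 | 12 | 0.80% (0.51 to 1.19) |

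The plan has no figure of its own to reproduce here. Protocol 3.2 says that the 3,000 target has no statistical basis.

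**The case against.** **The duty is not explicit.** Section 10.4.1 asks only for separate compilation. It does not mention any causality, a patient total or a rate. Table 2.4.7 is a separate compilation, and Protocol 3.2 states the background rate as one of bleeding-related ADRs. The laboratory sentence in 9.6 governs data collection, not analysis. This stands as a limit on confidence. It does not remove the point, because the instruction sits in the AE section and the protocol names ADRs in the next section when it means them.

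**A reader might infer that bleeding judged not related disappears.** It does not. Each PT stays visible in 2.4.3, by causality in 2.4.6 and, if serious, in 2.4.37. Unevaluable bleeding is already in 2.4.7.

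**A reader might infer that the total could lie anywhere from the largest PT row up to the sum of rows**, 6 to 17 in the illustration. That ignores 2.4.7, whose ADR patient count raises the floor to 12. SOC-level counts may narrow the range further.

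**A reader might infer that 2.4.21 breaches the protocol.** It does not: 10.4.2 asks for ADRs by concomitant medication.

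**The effect may be nil.** With g = 0 nothing is missing, and no document figure rules that out. This also stands.

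**Conclusion.** The gap is real and modest. The current SAP has no table with one de-duplicated number and rate of patients with any bleeding-related AE, although bleeding is the priority item and the AE section of the protocol asks for separate compilation. The planned outputs allow only a range for that total (12 to 17 patients in the illustration).

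The number missing runs from about 0 to 12 patients for g between 0% and 50%. This rests on three assumptions: that the 0.4% carries over from the EPA products, that it is a share of patients, and that g lies in that range. A reader might take the table of scenarios as showing that the bleeding rate will be materially understated. The documents do not support that, because they say nothing about g. Confidence is medium, since the any-causality reading of 10.4.1 is the most natural one but is not written out.

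**What to change.** Keep 2.4.7 and 2.4.21 unchanged. Add one table for safety-evaluable patients covering all bleeding-related AEs (SMQ 20000038, narrow scope, any causality), giving:

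- the number and rate of patients, each counted once;
- the number of patients classed Related, Unevaluable and Not related, with the priority order of 2.4.6 applied across all of a patient's bleeding events.

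The three classes then add up to the total, and Related plus Unevaluable equals the patients with bleeding ADRs, which gives a built-in check.

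Two additions are optional. One is an exact two-sided 95% interval for the rate; the current SAP specifies no interval for any safety proportion. The other is an AE version of 2.4.21; no protocol passage requires it, and without a control arm it could not separate a Drug effect from bleeding due to the co-medication.

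The cost is one extra table and a short SAP edit. The data are already collected and coded.
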